#### **7.2.4 Additional exclusion criteria during or at the end of the Run-in phase before randomization**

- E 33. Patients unwilling or unable to perform self-monitoring of blood glucose (SMBG), complete the patient diary or comply with study visits and other procedures as required per protocol.
- E 34. Patients insufficiently compliant during Run-in phase. Noncompliance will be based on tablet count (<80%) or based on the opinion of the Investigator.
- E 35. Informed consent withdrawal before randomization (patient who is not willing to continue or fails to return).
- E 36. Any clinically significant abnormality identified on physical examination, laboratory tests, electrocardiogram (ECG) or vital signs at the time of screening or any AE during screening period which, in the judgment of the Investigator or any Sub-investigator, would preclude safe completion of the study or constrains efficacy assessment.
- E 37. Lower extremity complications (such as skin ulcers, infection, osteomyelitis, and gangrene) identified during the Screening period, and still requiring treatment at Randomization.

## 8 STUDY TREATMENTS

### 8.1 INVESTIGATIONAL MEDICINAL PRODUCT(S)

The IMPs are sotagliflozin 400 mg, sotagliflozin 200 mg, and matching placebos. Patients will be provided with:

- Run in kit containing 1 wallet of 34 placebo tablets (identical to sotagliflozin 200 mg in appearance) for the Run-in phase
- Treatment kit containing 2 wallets of 38 tablets each (identical to sotagliflozin 200 mg in appearance) will be dispensed as needed for the duration of the treatment period in a double-blind manner.

Table 1 provides a summary of each IMP (dose and timing).

**Table 1 - Summary of investigational medicinal products during treatment period**

IMP:	Sotagliflozin (200 mg group)	Sotagliflozin (400 mg group)	Placebo group
Name of the IMPs	Sotagliflozin (SAR439954)	Sotagliflozin (SAR439954)	Placebo
Pharmaceutical form	Sotagliflozin (SAR439954) will be supplied as 200 mg tablets	Sotagliflozin (SAR439954) will be supplied as 200 mg tablets	Placebo will be supplied as tablets (identical to sotagliflozin in appearance)
Dose, timing and route of administration	
Sotagliflozin 200 mg group:
 
One 200 mg tablet, taken orally once daily, before first meal of the day
 
One placebo tablet, taken orally once daily, before first meal of the day
	
Sotagliflozin 400 mg group:
 
Two 200 mg tablets, taken orally once daily, before first meal of the day
	
Placebo group:
 
Two placebo tablets, taken orally once daily, before first meal of the day

Duration of treatment	52 weeks following randomization		
Storage conditions	Store between +15°C and +30°C (59°F and 86°F)		

IMP = investigational medicinal product

#### 8.1.1 Dose reduction

The dose maintenance will be handled according to the renal function assessed by the creatinine measurement throughout the study. If at any visit after randomization there is a rise in creatinine level (see details in Section 10.6.2), the Investigator should ensure that no reasonable explanation exists for creatinine increase. Sites will be notified by central laboratory alert if a patient has a >50% increase from Baseline level or >50% above the mean of creatinine values from the last 2 visits, where Baseline level is defined as the mean of creatinine values obtained at Screening and Randomization. The IMP should be stopped for 2 weeks. If at creatinine recheck the patient

has returned to the below threshold then IMP will be restarted at a reduced dose (ie, dose reduced via IRT to 200 mg for patients randomized to 400 mg, maintained to 200 mg for patients randomized to 200 mg, and to placebo for those randomized to placebo). Since IMP received is blinded, patients must return to the site and IRT will be contacted for this IMP re-initiation. Dose reduction can only be obtained at on-site visit by IRT. If the creatinine does not return to below the threshold, the IMP will be permanently discontinued but the patient will be asked to continue attending all study visits.

## 8.2 NONINVESTIGATIONAL MEDICINAL PRODUCT(S)

Noninvestigational medicinal product (NIMP) treatment is defined as the rescue medication(s) that will be used to treat hyperglycemia when a patient's hyperglycemia reaches the rescue threshold (see [Section 8.2.1](#) for details).

### 8.2.1 Rescue therapy

The thresholds values are defined as follows, depending on study period:

- From Baseline Visit (V3, Day 1) to Visit 8 (Week 8) (including value at Visit 8): FPG >270 mg/dL (15.0 mmol/L)
- From Visit 8 (Week 8) to Visit 9 (Week 12) (including value at Visit 9): FPG >240 mg/dL (13.3 mmol/L)
- From Visit 9 (Week 12) up to the EOT Period Visit 13 (Week 52) (including value at Visit 13): FPG >200 mg/dL (11.1 mmol/L) or HbA1c  $\geq 8.5\%$  (the 8.5% criterion does not apply if the HbA1c decrease from Baseline was  $\geq 1.0\%$ ).

Routine fasting SMBG (SMBG will be presented as equivalent self-monitoring plasma glucose [SMPG]) and central lab alerts on FPG (and HbA1c at Week 12 and onwards) are set up to ensure that glycemc parameters remain under predefined thresholds:

- If one fasting SMBG value exceeds the specific glycemc limit on 1 day, the patient checks it again during the 2 following days. If all the values in 3 consecutive days exceed the specific limit, the patient should contact the Investigator and **a central laboratory FPG measurement** (and HbA1c at Week 12 and onwards) **is performed** as soon as possible, preferably within 7 days to confirm the hyperglycemia.
- Upon receipt of a central laboratory rescue alert **a central laboratory re-test must be completed and confirmed as exceeding the criterion** for rescue before rescue therapy is initiated. The re-test confirmation should be performed as soon as possible, but within 7 days of receipt by unscheduled visit.

In the event that a confirmatory FPG and/or HbA1c exceed the threshold, the Investigator should ensure that no reasonable explanation exists for insufficient glucose control and in particular that:

- The increased FPG has been tested at a fasting status (ie, no food intake for  $\geq 8$  hours)
- Investigational product is given at the planned dose

- There is no intercurrent disease, which may jeopardize glycemic control (eg, infectious disease)
- Compliance to treatment is appropriate
- Compliance to diet and lifestyle is appropriate.

If any of the above can reasonably explain the insufficient glycemic control, the Investigator should consider not initiating rescue medication and should undertake appropriate action, ie:

- Assess plasma glucose in fasting condition (ie, after at least 8 hours fast)
- Initiate an evaluation and treatment of intercurrent disease (to be reported in AE/concomitant medication parts of the electronic case report form (e-CRF) and the medical record)
- Stress on the absolute need to be compliant with treatment
- Organize a specific interview with the patient and a Registered Dietician or other qualified nutrition professional and to reinforce on the absolute need to be compliant to diet and lifestyle recommendations, and schedule an FPG/HbA1c assessment at the next visit.

If none of the above mentioned reasons can be found, or if appropriate action fails to decrease FPG/HbA1c under the threshold values, rescue medication may be introduced (17).

- Open label rescue medication(s) to treat hyperglycemia must be in accordance with local standard of care and prescribing practice for patients with CKD and will be at the discretion of the investigator. Except for SGLT2 inhibitors and medications with specific contraindications in renal impairment, any approved medication(s) including oral antidiabetic drugs or insulin can be considered with appropriate dose modification as indicated.
- The patient continues the IMP (blinded) and stays in the study in order to collect efficacy and safety information. The planned visits and assessments should occur until the last scheduled visit
- Rescue therapy is considered an NIMP. Rescue therapy is to be reported in the e-CRF. This information should include specific drug name, dose, route of administration, and frequency.

If not covered by health insurance, the cost of the rescue therapy will be reimbursed by the Sponsor where permitted by local regulations.

### **8.3 BLINDING PROCEDURES**

#### **8.3.1 Methods of blinding**

To maintain blinding sotagliflozin and their matching placebo tablets (including packaging) will be blinded and indistinguishable.

During the double-blind Treatment Period, each treatment package will be labeled with a number, which is generated by a computer program from the Sanofi. Investigators will not have access to the randomization (treatment) code except under circumstances described in [Section 8.3.2](#).

The randomization and the treatment allocation will be performed centrally by an IRT. The study biostatistician provides the randomization scheme to the IRT. Then, the IRT generates the patient randomization list from which it allocates treatment arms to the patients.

Fasting glucose (plasma or serum) and HbA1c will be masked to study sites and patients after randomization and until study end. To prevent partial unblinding, UGE and UGCR results will be masked to study sites and patients. Additionally, urinalysis by dipstick will not include the measurement of urine glucose.

Quantitative urine glucose, albumin, calcium, phosphorus, magnesium, and creatinine will be measured separately at selected on-site visits by the central laboratory.

The CEC members will perform adjudication in a blinded manner.

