	
if at any visit after Week 8 there is a rise of >50% above the mean of creatinine values from the previous 2 visits, the Investigator should ensure that no reasonable explanation exists for creatinine increase and in particular the following causes:
 
 
• Medications that increase creatinine
 
• Decrease in cardiac output
 
• Obstructive uropathy
 
• Urinary tract infection
 
• Volume depletion
 
 
If addressing these causes does not reduce the creatinine level below the above stated threshold, the investigational medicinal product (IMP) will be stopped for 2 weeks. If at creatinine recheck the patient has returned to below the threshold, then IMP will be restarted at a reduced dose (ie, dose reduced via interactive response technology (IRT) to 200 mg for those randomized to 400 mg; maintained to 200 mg for those randomized to 200 mg, and to placebo for those randomized to placebo). If the creatinine does not return to below the threshold, the IMP will be permanently discontinued but the patient will be asked to continue attending all study visits.
 
Patients will be randomly assigned 1:1:1 to 1 of 3 treatment groups:
 
 
A. Placebo;
 
B. Sotagliflozin 200 mg
 
C. Sotagliflozin 400 mg
 
 
The HbA1c and FPG results will be masked to study sites and patients after randomization and until study end. To prevent partial unblinding, UGE and urine glucose:creatinine ratio (UGCR) results will be also masked to study sites and patients.
 
Additionally, urinalysis by dipstick will not include the measurement of urine glucose. Quantitative urine glucose, albumin, calcium, and creatinine will be measured separately at selected on-site visits by the central laboratory.
 
Early Termination
 
If a patient discontinues treatment with IMP early during the Treatment Period, the patient will have a Premature end of treatment (EOT) Visit, and a Follow-up Visit 4 weeks after the last dose of IMP. In addition, every effort will be made to have all patients return to the site at the time corresponding to their scheduled visits, particularly the Weeks 26 and 52 visits.
 
If the patient does not agree to site visits, they will be contacted by telephone to enquire about safety status, particularly at the time of the initially scheduled end of study.
 
The study design is presented graphically in Section 1.1.

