### **6.1.2 Double-blind Treatment Period (Day 1 to Week 26)**

Eligible patients will be randomized on Day 1 (Visit 3). In order to qualify for randomization, patients must also demonstrate compliance during the single-blind placebo Run-in Phase based upon tablet count ( $\geq 80\%$ ) and, as assessed, at the Investigator's discretion.

Randomization will be stratified by:

- HbA1c at Screening ( $\leq 8.5\%$  and  $> 8.5\%$ )
- SBP at Screening ( $< 130$  mmHg,  $\geq 130$  mmHg).

Following randomization, patients will be treated in a double-blind manner for 26 weeks. A total of 276 patients  $\geq 18$  years of age (or  $\geq$  legal age of the majority, whichever is greater) are planned to be randomly assigned 1:1:1 to the following treatment groups:

- Placebo, given as 2 placebo tablets (identical to sotagliflozin 200 mg in appearance), once daily
- Sotagliflozin 200 mg, given as 2 tablets: 1 sotagliflozin 200 mg tablet and 1 placebo tablet (identical to sotagliflozin 200 mg in appearance), once daily
- Sotagliflozin 400 mg, given as 2 sotagliflozin 200 mg tablets, once daily.

Fasting glucose (plasma or serum) and HbA1c results will be masked to study sites and patients after randomization until study end. To prevent partial unblinding, UGE and UGCR will be masked to study sites and patients, and the central laboratory urine dipstick will not include the measurement of urine glucose.

Quantitative urine glucose, albumin, calcium, and creatinine will be measured separately at selected on-site visits by the central laboratory.

All visits will be on-site visits.

If a patient discontinues treatment with investigational medicinal product (IMP) early during the Treatment Period, the patient will have a premature end of treatment (EOT) Visit and a Follow-up Visit, 4 weeks ( $\pm 5$  days) after the last dose of IMP. In addition, every effort will be made to have all patients return to the site at the time corresponding to their scheduled visits, particularly the Weeks 26 and 52 Visits.

If a patient does not agree to site visits, he/she will be contacted by telephone to inquire about their safety status, particularly at the time of the initially scheduled end of study.

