#### **9.1.4.5 Kidney function parameter assessments**

Serum creatinine and urine albumin, protein, calcium, creatinine, phosphorus, magnesium, and glucose will be assessed at Baseline (Visit 3) and at selected on-site visits (see [Section 1.2](#)). A central laboratory will analyze samples and estimate change from Baseline in UACR, UGE, UGCR, serum creatinine, and eGFR. To prevent partial unblinding, UGE and UGCR results will be masked to study sites.

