#### **9.1.4.6 Fructosamine, cystatin C, and NT-proBNP measurements**

Fructosamine is measured in the fasting state at Baseline (Visit 3) and all on-site visits during the treatment period with the exception of Week 1 (Visit 4), Week 2 (Visit 5), and Week 3 (Visit 6).

Cystatin C and NT-proBNP are measured in the fasting state at Baseline (Visit 3) and all on-site visits during the treatment period with the exception of Weeks 8 and 18 (Visits 8 and 10). In addition, cystatin C is also to be measured at Week 56 (Visit 14).

For the eligibility and efficacy assessments of the study, fructosamine, cystatin C, and NT-proBNP are measured at a central laboratory to allow estimation of change from Baseline to Week 26.

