## 9.5 APPROPRIATENESS OF MEASUREMENTS

Sotagliflozin monotherapy in patients with T2D who have inadequate glycemic control with diet and exercise is expected to lower HbA1c over 26 weeks of treatment (primary efficacy analysis). Sotagliflozin treatment for 26 weeks is likely to be of sufficient duration to observe effects on reduction of HbA1c, BP, and body weight, and is therefore selected as the timepoint for assessment of the primary endpoint HbA1c. Treatment up to 52 weeks will provide additional long-term data on safety and efficacy.

The concentration of HbA1c reflects the glycemic history of the previous 120 days and is thus an index of mean glycemia, documenting glycemic control over the past 2 to 3 months. Hemoglobin A1c has also been shown to correlate with the development of long-term complications of diabetes, and reduction of HbA1c is known to reduce the risk of long-term microvascular complications. Therefore, HbA1c is considered an appropriate primary endpoint for assessing the effect of a treatment on glycemic control. The duration of study treatment (26 weeks for the primary HbA1c endpoint) is considered to be sufficient for achieving stable conditions with IMP and for enabling an adequate assessment of time-dependent changes in HbA1c, as well as changes in fructosamine.

The problem of weight gain in T2D is widely recognized. More than 80% of individuals with T2D are overweight, many at the time of diagnosis. Consequently, iatrogenic weight gain is not only unwelcome, but represents an important clinical issue that can become a barrier to the successful management of glycemic control. Therefore, in this study assessing change in body weight from Baseline to Week 26 is a secondary endpoint.

Improvements in FPG have been observed with sotagliflozin in multiple studies. Therefore assessment of fasting prandial glucose is relevant in this study. These 2 parameters are also considered by regulatory agencies to be supportive of efficacy of an antidiabetic agent.

The other efficacy and safety assessments in this study are standard, well-established measurements for a Phase 3 study evaluating the treatment of T2D in adult participants.

The length of the study is considered appropriate for detection of the primary endpoint given the power estimates (see [Section 11](#)).

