## 10 STUDY PROCEDURES

### 10.1 VISIT SCHEDULE

The visit schedule and procedures/assessments are listed in the Study Flow Chart ([Section 1.2](#)). The aim of this section is to provide details on how some of the procedures/assessments should be performed.

This is an out-patient study and consists of 14 on-site visits, although optional on-site and/or telephone visits can be scheduled at any time for any reason during the study whenever considered necessary by the Investigator.

The patients need to be fasting for on-site visits Visit 1 through Visit 13 (Week -4 through Week 52), unless instructed otherwise by the Investigator. Throughout the study, “fasting” is defined as 8 hours without food. **Note:** If the patient is not fasting at the visits specified above, the blood sample will not be collected and a new appointment should be given to the patient for the following day if possible, with instruction to be fasted (other procedures can be performed as scheduled). All laboratory assessments will occur prior to IMP administration on the day of the visit.

The Run-in visit (Visit 2) can be performed as soon as the results of all screening tests are available and the patient is confirmed to be eligible for participation in the study. The visit window for on-treatment Visit 4 through Visit 12 is  $\pm 5$  days. Visits 13 (EOT) should occur at the scheduled timepoint  $\pm 5$  days. For the Follow-up (Visit 14), the visit window should occur within  $\pm 5$  days, 4 weeks after last dose of IMP.

If one visit date is changed, the next visit should occur according to the original schedule, ie, calculated from the date of Baseline visit (Visit 3, Week 0).

For a complete list of procedures scheduled for each study visit please refer to the Study Flowchart ([Section 1.2](#)), which details the procedures to be performed.

All data obtained during the trial visits are reviewed by the Investigator and Sub-Investigators who are qualified in treatment of T2D and are trained on the study.

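### The protocol masks HbA1c, fasting glucose and urine glucose results but nowhere masks fructosamine, so as written this serial glycaemic endpoint is open to sites; the added risk to the blind is probably modest.

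*Protocol*

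**What the plan says.** Protocol 8.3.1 (Methods of blinding) states: "Fasting glucose (plasma or serum) and HbA1c will be masked to study sites and patients after randomization and until study end". It continues: "To prevent partial unblinding, UGE and UGCR results will be masked to study sites and patients", and it leaves glucose off the urine dipstick. Section 6.1.2 masks the same results. The synopsis does too, though it refers to FPG rather than to plasma or serum glucose: "The HbA1c and FPG results will be masked to study sites and patients after randomization and until study end". Section 9.1.4.5 repeats the masking for UGE and UGCR only, and for sites only.

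On fructosamine, section 9.1.4.6 says: "Fructosamine is measured in the fasting state at Baseline (Visit 3) and all on-site visits during the treatment period". Weeks 1, 2 and 3 are excepted, and the assay is done centrally. Protocol 9.1.3 and SAP 2.1.3.3 list its change from Baseline to Week 26 among the other efficacy endpoints. Section 9.5 names it beside HbA1c, describing the treatment period as long enough for "enabling an adequate assessment of time-dependent changes in HbA1c, as well as changes in fructosamine".

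On who sees visit data, section 10.1 says: "All data obtained during the trial visits are reviewed by the Investigator and Sub-Investigators".

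**The concern.** The sponsor evidently wanted sites to be unable to follow a patient's glycaemic response by laboratory result. It masked fasting glucose and HbA1c, then closed indirect routes as well: UGE, UGCR and dipstick glucose. Fructosamine is the one remaining central-laboratory glycaemic marker, and the documents give no reason for leaving it off the list.

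Several decisions before Week 26 rest on site judgment:
- whether to start rescue once the criteria are met, and with which drug (8.2.1);
- whether a safety concern warrants changing background therapy (8.8);
- how to respond to poor compliance (8.7.1);
- whether to stop study drug on the investigator's opinion (10.3.3);
- how to judge the causality of adverse events (10.4.2).

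The primary analysis keeps HbA1c values obtained after rescue or after stopping study drug (11.4.2.1), so any difference in management between arms would carry into the primary estimate. The proportion rescued by Week 26 is itself an endpoint (9.1.3).

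**Working it through.** The point rests mainly on comparing sections. One calculation bounds what a glycaemic result could reveal.

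**1. What is masked.**
- Synopsis: HbA1c, FPG, UGE, UGCR.
- 6.1.2 and 8.3.1: HbA1c, fasting glucose in plasma or serum, UGE, UGCR.
- 9.1.4.5: UGE and UGCR, to sites.
- SAP: nothing on masking fructosamine.

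Fructosamine appears in none of these.

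**2. When fructosamine is drawn.** The flow chart (1.2), 9.1.4.6 and the visit lists in 10.1 agree: Baseline, then Weeks 4, 8, 12, 18, 26, 39 and 52. That is 7 post-baseline draws, of which 4 (Weeks 4, 8, 12, 18) precede the Week 26 visit. The first comes 8 − 4 = 4 weeks before the first post-baseline HbA1c.

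**3. Whether sites see it.** Section 10.1 gives investigators all visit data. Read alone, it would release HbA1c too, so it works only as a default to which the masking lists are exceptions. Fructosamine is not among those exceptions. Silence in 9.1.4.6 shows little by itself, because the HbA1c and FPG assessment sections (9.1.4.1, 9.1.4.2) are also silent. What counts is its absence from the synopsis, 6.1.2 and 8.3.1.

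**4. Whether sites need it.** No eligibility criterion (7.1, 7.2), rescue threshold (8.2.1) or creatinine rule (10.6.2) uses fructosamine, and it is not in the safety laboratory table (Table 2).

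**5. What a glycaemic result could reveal.** The planning figures in 11.1 are a difference δ = 0.5%, SD σ = 1.2%, two-sided α = 0.05 and 92 per group for at least 80% power. They reproduce. By normal approximation n = 2σ²(1.960 + 0.842)²/δ² = 2 × 1.44 × 7.85 / 0.25 = 90.4, rounded up to 91. By the t test, power is 79.8% at 91 and 80.3% at 92. Now assume normal distributions with equal SD and a choice between two equal arms, 400 mg and placebo. A site knowing a patient's exact Week 26 HbA1c change would then name the arm correctly with probability Φ(δ/2σ) = Φ(0.5/2.4) = Φ(0.208) = 0.58, against 0.50 by chance. A marker that informs only through HbA1c would do no better, and the 200 mg arm makes guessing harder.

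**6. What sites already see.** Fasting self-monitoring is required at least 3 times a week from Run-in (flow chart, footnote f). It is entered in a diary that the site reviews at every visit from Visit 2 (9.2.1.7). From randomization to Week 26 that is at least 3 × 26 = 78 readings. Central alerts on FPG, and on HbA1c from Week 12, also reach the site (8.2.1, 9.1.4.7).

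**The case against.** The strongest reply is that little is lost. Release of fructosamine to sites is inferred, and a laboratory manual outside these documents may already withhold it. Self-monitored fasting glucose lets a site follow response before Week 4. Rescue requires a central-laboratory FPG or HbA1c value retested and confirmed above a fixed threshold (8.2.1), and background therapy may not change before rescue except for safety (8.8, 8.8.1). Treatment steered by fructosamine would therefore largely be a protocol deviation. HbA1c is assayed centrally, so any bias is indirect. Fructosamine itself is only summarised descriptively (11.4.2.3).

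Most of this stands, and it limits the size of the problem. It does not justify the omission. The sponsor masked FPG and HbA1c although self-monitoring and alerts were open, so those channels were not thought to make masking pointless. The 58% figure concerns guessing the arm; a site could also react to the result itself. That route is narrowed by the rescue and background-therapy rules but not closed, because some judgment remains.

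A reader might go further and conclude that sites in fact read each patient's response from Week 4. The documents do not say so; they only fail to prevent it.

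**Conclusion.** The omission is confirmed: every masking statement leaves out fructosamine, and under the protocol's default its results are open to sites, with four post-baseline values before the primary visit. This assumes that section 10.1 is the operative default and that no laboratory specification outside these documents withholds the results.

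The added risk to the blind is probably modest. A reader might want to express it as a given loss in the planned 0.5% HbA1c difference. The documents give no figure for how site behaviour would respond, so any such number would be an assumption and none is offered. The point merits action because the gap is plain and closing it is nearly free. There is no evidence here that the primary result is compromised.

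**What to change.** Add fructosamine to the results masked to sites and patients after randomization in the synopsis, 6.1.2 and 8.3.1. Put a matching sentence in 9.1.4.6, and have the central laboratory withhold it from site reports as it does HbA1c. If the laboratory already does this, the protocol sentence alone settles the matter. The cost is amendment wording and at most one report setting. The sample size and analysis do not change.

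SAP 1.6 records that the first-step analysis has already been run, and that analysis required Week 26 data on all patients. For this trial, an amendment made after that point cannot alter the period that matters, so the clinical study report should state whether sites received fructosamine results before Week 26.
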